6.5.8.3 Study Baseline

Baseline measures are defined as the last non-missing measure prior to the initiation of randomized study treatment as documented in the subject dosing diary. Per the schedule of assessments in the protocol, this is expected to be the Visit 1 value. Measurements that are obtained after the first dose of randomized study treatment will be considered post-baseline values. If a measurement of a variable is not made on a given subject prior to the first dose of randomized study treatment, then that subject will be considered not to have a baseline value for that variable. CFB is defined as post-baseline assessment minus baseline assessment.

6.5.8.4 CDISC Standards

The exchange and terminology standards outlined in Section 4 will be used to create SDTM domains and ADaM datasets. A reviewer's guide and define.xml will be produced for each set. The ADaM datasets will be used to support all tables, listings, and figures with the exception of the pregnancy results listing which will be generated from SDTM. All data in the ADaM datasets will be used as the population for listings. At least one listing will be created for each ADaM dataset to display (a) most collected variables, and (b) derived variables used in the tables and figures. The source listing(s) will be referenced in all table and figure footnotes.

6.5.8.5 Adjustment for Covariates

The primary endpoints are CFB in total corneal fluorescein staining (NEI scale) at Day 57 and CFB of Dryness Score (VAS) at Day 57. The two primary endpoints will be analyzed separately using an ANCOVA model with baseline measurement as a numeric covariate and treatment as the main effect.

Subject randomization is stratified by clinical site and dryness score <70 vs ≥ 70 (VAS) at baseline (Visit 1). The analyses will not be adjusted for the stratification factors.

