10.4.5 Primary Efficacy Analyses

The primary comparisons in this trial will be between NOV03 versus saline at Day 57 in the FAS with available data per subject using the following estimands:

- Population: Subjects with DED defined through enrollment criteria
- Endpoint:
 - CFB in tCFS in the study eye at Day 57
 - CFB of Dryness Score (VAS) at Day 57
- Intercurrent event:
 - Discontinuation of study medications is ignored. [treatment policy strategy]
 - Non-optimal compliance is ignored. [treatment policy strategy]

- Withdrawal due to any reason. Missing data not imputed. [hypothetical strategy]
- Population-level summary:
 - Difference in the mean CFB in tCFS in the study eye at Day 57 between NOV03 and saline.
 - Difference in the mean CFB of Dryness Score (VAS) at Day 57 between NOV03 and saline.

If the overall study discontinuation rate is $\geq 5\%$ then the primary analysis will be based on imputation methodology using the following estimands and the available data analyses will become robustness analyses.:

- Population: Subjects with DED defined through enrollment criteria
- Endpoint:
 - CFB in tCFS in the study eye at Day 57
 - CFB of Dryness Score (VAS) at Day 57
- Intercurrent event:
 - Discontinuation of study medications is ignored. [treatment policy strategy]
 - Non-optimal compliance is ignored. [treatment policy strategy]
 - Withdrawal due to lack of efficacy or adverse events. Baseline observation carried forward (BOCF) is used to impute missing data [hypothetical strategy].
 - Missing data without withdrawal or withdrawal due to reasons other than lack of efficacy or adverse events. Multiple imputations using randomized treatment-based Markov Chain Monte Carlo is used to impute missing data [hypothetical strategy].
- Population-level summary:
 - Difference in the mean CFB in tCFS in the study eye at Day 57 between NOV03 and saline.
 - Difference in the mean CFB in Dryness Score (VAS) at Day 57 between NOV03 and saline.

The primary comparison in this trial will be between NOV03 versus saline at Day 57. The primary efficacy endpoints (e.g. CFB in total corneal fluorescein staining [NEI scale] and Dryness Score) will be tested using hierarchical fixed sequence testing and summarized descriptively (n, mean, standard deviation, median, min, and max) and analyzed separately using an ANCOVA model with terms for baseline value, and treatment.

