6.1.2 Trial Procedures

The schedule of assessments, as outlined in the trial protocol, is presented below in Table 1.

Table 1. Schedule of Assessments

Procedure	Visit 0 Within 14 days before Visit 1 (Day -14 to -1)	Visit 1 Day 1	Visit 2 Day 15 ± 1	Visit 3 Day 29 ± 2	Visit 4 / (ET) Day 57 ± 2
Informed Consent / HIPAA	X				
Demographics	X				
Medical/Surgical History	X	X			
Previous/Concomitant Medication	X	X	X	X	X
Inclusion/Exclusion Criteria	X	X			
Urine Pregnancy Test	X	X			X
Eyedrop Acceptability Questionnaire					X
Dryness Score (VAS severity of dryness)*		X	X	X	X
VAS*		X	X	X	X
OSDI*	X	X	X	X	X
Eyedrop Acceptability Questionnaire*					X
Visual Acuity (ETDRS)	X	X	X	X	X
Slit-Lamp Biomicroscopy	X	X	X	X	X
TFBUT*	X	X			X
Corneal Fluorescein Staining (NEI scale)*	X	X	X	X	X
Meibomian Gland Assessment (MGD score)*	X	X			X
Schirmer's Test I (without anesthesia)*	X	X			X
Intraocular Pressure	X				X
Dilated Fundoscopy	X				X
Randomization (via IRS)		X			
In-office instillation of randomized IMP		X			
Instillation Comfort Questionnaire		X			
Adverse Event Query	X	X	X	X	X
Dosing Diary Dispensation and/or Review		X	X	X	X
Dispensation of trial medication		X	X	X	

Procedure	Visit 0 Within 14 days before Visit 1 (Day -14 to -1)	Visit 1 Day 1	Visit 2 Day 15 ± 1	Visit 3 Day 29 ± 2	Visit 4 /(ET) Day 57 ± 2
-----------	--	------------------	-----------------------	-----------------------	-----------------------------

Collection of trial medication

X

X

X

Trial Exit

X

*=Assessment to be conducted in the order as depicted in the Schedule of Assessments; ETDRS = Early Treatment of Diabetic Retinopathy Study; HIPAA = Health Information Portability and Accountability Act; NEI = National Eye Institute; OSDI = Ocular Surface Disease Index; TFBUT = Tear Film Break Up Time; ET = Early Termination; VAS: burning/stinging, sticky feeling, foreign body sensation, itching, blurred vision, sensitivity to light, pain, frequency of dryness, and awareness of dry eye symptoms

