6.2.1 Inclusion Criteria

1. Be at least 18 years of age at the time of consent.
2. Provide written informed consent.
3. Have a subject reported history of Dry Eye Disease in both eyes for at least 6 months prior to Visit 0.
4. Have TFBUT ≤ 5 sec at Visit 0 and Visit 1.
5. Have OSDI ≥ 25 at Visit 0 and Visit 1.
6. Have an unanesthetized Schirmer's Test I ≥ 5 mm at Visit 0 and Visit 1.
7. Have MGD defined as total MGD score ≥ 3 (secretion of 5 central glands on lower eyelid will be evaluated, each will be scored from 0-3; 0 = normal, 1 = thick/yellow, whitish, particulate 2 = paste; 3 = none/occluded; total score will range from 0-15) at Visit 0 and Visit 1.
8. Have a total corneal fluorescein staining score of $4 \leq X \leq 11$ (i.e. sum of inferior, superior, central, nasal, and temporal) according to the NEI scale at Visit 0 and Visit 1.
9. Have at least one eye (the same eye) satisfy all criteria for 4, 6, 7, and 8 above at Visit 0 and Visit 1.
10. Be able and willing to follow instructions, including participation in all trial assessments and visits.

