**6.5.7.6 Sensitivity Analyses****6.5.7.6.1 Sensitivity Analyses for Primary Efficacy Endpoints**

Two-sample t-tests (equal variance assumed), Wilcoxon rank sum tests and mixed-effect repeated measures analysis comparing treatment groups will be performed as sensitivity analyses. The mixed-effect repeated measures model will include treatment, baseline value, visit, and the interaction between treatment and visit as fixed effects, and subject as a random effect. An unstructured covariance matrix will initially be used to model the covariance among repeated measures; however, if the model fails to converge using this covariance structure, either heterogeneous TOEPLITZ, homogeneous TOEPLITZ, or compound symmetry will be implemented according to the Akaike information criterion with a correction for finite sample sizes (AICc).

Sample SAS two-sample t-test code:

```
PROC TTEST DATA=INDATA;
  CLASS <TREATMENT>;
  VAR <ENDPOINT>;
RUN;
```

Sample SAS Wilcoxon rank sum test code:

```
PROC NPAR1WAY DATA=INDATA WILCOXON;
  CLASS <TREATMENT>;
  VAR <ENDPOINT>;
RUN;
```

Sample SAS mixed-effect repeated measures analysis code:

```
PROC MIXED DATA=INDATA;
  CLASS <TREATMENT> <VISIT>;
  MODEL <ENDPOINT>=<TREATMENT> <VISIT> <TREATMENT>*<VISIT> <BASELINE>;
  REPEATED <VISIT> / SUBJECT=<SUBJECT> TYPE=UN;
  RANDOM <SUBJECT>;
```

```
ESTIMATE 'NOV03-SALINE' <TREATMENT> -1 1 / ALPHA=0.05 CL;  
RUN;
```

Where 'Saline' is <TREATMENT>=0 and 'NOV03' is <TREATMENT>=1.

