6.5.10 Determination of Sample Size

The statistical hypotheses for the primary endpoint of CFB corneal fluorescein staining (NEI scale) total score at Day 57 are as follows:

H_{01} : The difference, between study eyes treated with NOV03 and study eyes treated with saline, in the mean CFB corneal fluorescein staining (NEI scale) total score at Day 57 = 0.

H_{A1} : The difference, between study eyes treated with NOV03 and study eyes treated with saline, in the mean CFB corneal fluorescein staining (NEI scale) total score at Day 57 \neq 0, with superiority claimed if the difference is less than 0 (NOV03 minus saline).

The statistical hypotheses for the hierarchical primary endpoint of the CFB Dryness Score at Day 57 are as follows:

H_{02} : The difference, between subjects treated with NOV03 and subjects treated with saline, in the mean CFB Dryness Score at Day 57 = 0.

H_{A2} : The difference, between subjects treated with NOV03 and subjects treated with saline, in the mean CFB Dryness Score at Day 57 $\neq 0$, with superiority claimed if the difference is less than 0 (NOV03 minus saline).

Two hundred fifty (250) subjects (study eyes) per treatment group yields 97.9% power to reject H_{01} in favor of H_{A1} and conclude superiority of NOV03 over saline in the mean CFB tCFS score at Day 57 assuming a true difference (NOV03 minus saline) of -1.0, a common standard deviation of 2.8, and a two-sided alpha = 0.05. Two hundred fifty (250) subjects per treatment group yields 97.9% power to reject H_{02} in favor of H_{A2} and conclude superiority of NOV03 over saline in the mean CFB Dryness Score (VAS) at Day 57 assuming a true difference (NOV03 minus saline) of -10, a common standard deviation of 28, and a two-sided alpha = 0.05. Accounting for an assumed 10% subject discontinuation rate, approximately 560 subjects (280 subject each arm) will be randomly assigned to trial treatment such that approximately 250 evaluable participants per arm complete the trial.

Therefore, assuming independence between tCFS score and Dryness Score (VAS), 250 FAS subjects per treatment group at Day 57 yields $97.9\% * 97.9\% = 95.8\%$ power to reject both H_{01} and H_{02} . A positive correlation between these two endpoints would increase the overall power.

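### The models for the three alpha-controlled symptom endpoints adjust only for the endpoint's own baseline; adding baseline OSDI, already collected, might gain a little precision at negligible cost

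*SAP*

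**What the plan says.** Protocol 10.4.5 and SAP 6.5.7.3 analyse each primary endpoint with an "ANCOVA model with terms for baseline value, and treatment". SAP 6.5.8.5 repeats this as "an ANCOVA model with baseline measurement as a numeric covariate and treatment as the main effect" and adds: "The analyses will not be adjusted for the stratification factors". The Protocol synopsis has quantitative secondary endpoints analysed in the same way as the primary. For the repeated-measures sensitivity analysis, SAP 6.5.7.6.1 states: "The mixed-effect repeated measures model will include treatment, baseline value, visit, and the interaction between treatment and visit as fixed effects". The endpoint's own baseline is therefore the only baseline covariate in either model.

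Baseline is the last non-missing value before the first dose, and SAP 6.5.8.3 adds: "Per the schedule of assessments in the protocol, this is expected to be the Visit 1 value". In the schedule (SAP 6.1.2, Protocol Appendix 1), the row beginning "Dryness Score (VAS severity of dryness" is marked once before treatment, at Visit 1. OSDI is marked at both Visit 0 and Visit 1, and the entry criterion in SAP 6.2.1 reads: "Have OSDI ≥ 25 at Visit 0 and Visit 1". The plan uses OSDI for eligibility, as a baseline summary and as an endpoint, but not as a covariate.

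**The concern.** The Dryness Score is a symptom rating. Its model uses one pre-treatment symptom value, while a second symptom instrument, a 12-question score, sits unused in the same database. If baseline OSDI predicts later Dryness beyond what baseline Dryness already predicts, including it would reduce the residual variance and narrow the confidence interval.

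The affected endpoints sit in a fixed sequence. Dryness Day 57 must be significant before any of the four secondary endpoints is tested, Dryness Day 15 stands before the next three, and burning/stinging Day 57 stands before central staining. The documents state power only for the two primary endpoints, so the margin at the two secondary symptom endpoints is unknown.

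**Working it through.** **Inputs.** SAP 6.5.10 plans the Dryness Score "assuming a true difference (NOV03 minus saline) of -10, a common standard deviation of 28, and a two-sided alpha = 0.05", with 250 per arm. The Protocol synopsis says that the NVU-002 estimate was -11 (SD 26), from an ANCOVA with baseline and treatment, and that -10 (SD 28) is a conservative choice. I therefore treat 28 as a residual SD already adjusted for baseline Dryness. The partial correlation r of baseline OSDI with Day 57 Dryness, given baseline Dryness and within arm, is not in the documents and is assumed. With baseline Dryness in the model, r is the same whether the response is the Day 57 score or the change from baseline.

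**Reproducing the plan.** SE = 28 × √(2/250) = 2.504, and 10/2.504 = 3.99. Two-sided power at 0.05 is 97.9% (normal 97.90%, noncentral t 97.86%), which matches the stated 97.9%. The joint figure 0.979 × 0.979 = 95.8% also matches.

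**Adding OSDI.** Residual SD = 28 × √(1 − r²). The information gained, in subjects per arm, is 250 × (1/(1 − r²) − 1). Power is by noncentral t; the -7 column is an assumed smaller effect.

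| r (assumed) | Variance cut | Residual SD | SE | 95% CI half-width | Equivalent subjects per arm | Power at -10 | Power at -7 |
|---|---|---|---|---|---|---|---|
| 0 | 0% | 28.0 | 2.504 | 4.91 | 0 | 97.9% | 79.7% |
| 0.1 | 1% | 27.9 | 2.492 | 4.88 | 2.5 | 98.0% | 80.1% |
| 0.2 | 4% | 27.4 | 2.454 | 4.81 | 10.4 | 98.2% | 81.3% |
| 0.3 | 9% | 26.7 | 2.389 | 4.68 | 24.7 | 98.7% | 83.3% |

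**What r might be.** Let a be the correlation of baseline with Day 57 Dryness, b that of OSDI with Day 57 Dryness, and c that of OSDI with baseline Dryness. Then r = (b − ac)/√((1 − a²)(1 − c²)). I tried a = 0.3, 0.4, 0.5; b = 0.2, 0.3, 0.4; c = 0.4, 0.5, 0.6, all assumed. Over the 27 combinations r runs from -0.14 to 0.32. The variance cut runs from 0 to 10.3% and is below 5% in 21 of them.

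**Cost if OSDI adds nothing.** With 500 subjects the current ANCOVA has 500 − 3 = 497 error degrees of freedom; the addition leaves 496. Power at r = 0 stays at 97.86% on the degrees of freedom alone. Chance imbalance in an uninformative covariate inflates the variance by about 1/496, or 0.2%, which brings power to about 97.84%.

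**The case against.** The strongest case is that nothing is wrong. Adjusting for the endpoint's own baseline is an ordinary, pre-specified choice, the test is valid, and it is the model from which the trial was sized. There is headroom as well: at the NVU-002 values (-11, SD 26) power with 250 per arm is about 99.7%. All of that stands, and it is why this is an optional improvement.

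Several stronger inferences are tempting, and the documents do not support them:

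- **That the Dryness VAS is noisy and precision is certainly being lost.** No VAS reliability and no OSDI–Dryness correlation are given. The gain may be zero, and the entry threshold of 25 narrows the OSDI range, which can weaken its predictive value.
- **That the two pre-treatment OSDI readings should be averaged.** The mean departs from the SAP's last-value baseline rule. It also mixes in a visit before the eye-drop restriction, which applies from 24 hours before Visit 1 (Protocol 5.4, exclusion 15, and 8.2).
- **That every randomised subject has OSDI.** Eligibility guarantees it only for correctly enrolled subjects. The FAS is everyone randomised and dosed, including anyone enrolled in error.
- **That one model term is the whole change.** The sample size assumes 10% discontinuation, above the 5% trigger for imputation. On that branch the imputation model must contain OSDI too, or it will not match the analysis model.

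It is also fair that OSDI is not the only candidate: nine further VAS items are recorded at Visit 1. The case for OSDI is that entry requires it, so missing values should be rare, and that it is a multi-item score. That makes it a reasonable choice, not a proven best one.

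**Conclusion.** The point holds as a small, optional gain in efficiency. The ANCOVA and repeated-measures models for Dryness Day 57, Dryness Day 15 and burning/stinging Day 57 leave out a baseline symptom score that the trial already collects. For Dryness Day 57, assumed partial correlations of 0 to 0.3 give 0 to 9% less residual variance and at most 0.8 percentage points of power at the planned effect. At a difference of -7 the gain is at most about 3.6 points (79.7% to 83.3%). No size can be given for the two secondary endpoints, because the documents state no effect or SD for them. The result rests on the assumed r and on SD 28 being a baseline-adjusted residual SD. It implies no bias, no invalid test and no shortfall in sample size.

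**What to change.** Before unmasking, in SAP 6.5.7.3, 6.5.7.6 and 6.5.8.5 and in Protocol 10.4.5 (with the synopsis brought into line):

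1. Add baseline OSDI as one further continuous covariate in the ANCOVA and the repeated-measures model for Dryness Day 57, Dryness Day 15 and burning/stinging Day 57. Keep the endpoint's own baseline in each model.
2. Define it by the SAP's existing rule: the last non-missing value before the first dose, normally Visit 1 and otherwise Visit 0. State how a subject with neither value is handled, so that none drops out of the FAS analysis.
3. Include OSDI in the multiple-imputation model for these endpoints, used if discontinuation is 5% or more. The sample code in SAP 6.5.7.3 is written for staining regions limited to 0–3, so a symptom-score version has to be written in any case.

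The cost is one error degree of freedom and small edits to the protocol, SAP and code; no new data are needed. The sponsor could first estimate the partial correlation in NVU-002, where both OSDI and VAS were measured (Protocol 4.6), and leave the model as it is if r is close to zero.

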The statistical hypotheses for the hierarchical primary endpoint of the CFB Dryness Score (VAS) at Day 57 are as follows:

H_{02} : The difference, between subjects treated with NOV03 and subjects treated with saline, in the mean CFB Dryness Score (VAS) at Day 57 = 0.

H_{A2} : The difference, between subjects treated with NOV03 and subjects treated with saline, in the mean CFB Dryness Score (VAS) at Day 57 $\neq 0$, with superiority claimed if the difference is less than 0 (NOV03 minus saline).

The study has been designed to have 95% power to reject both H_{01} and H_{02} assuming independence between the sign and symptom endpoint; positive correlation between these two endpoints would increase the overall power.

Estimated mean differences (common standard deviations) in CFB to Day 57 using an ANCOVA analysis with CFB to Day 57 as the response, baseline as a covariate and treatment as the fixed effect from NVU-002 are: -1.2 (2.5) for tCFS and -11 (26) for Dryness Score. Conservative estimates of -1.0 (2.8) for tCFS and -10 (28) for Dryness Score are used for sample size calculation.

Two hundred fifty (250) subjects (study eyes) per treatment group yields 97.9% power to reject H_{01} in favor of H_{A1} and conclude superiority of NOV03 over saline in the mean CFB tCFS score at Day 57 assuming a true difference (NOV03 minus saline) of -1.0, a

common standard deviation of 2.8, and a two-sided alpha = 0.05. Two hundred fifty (250) subjects per treatment group yields 97.9% power to reject H_{02} in favor of H_{A2} and conclude superiority of NOV03 over saline in the mean CFB Dryness Score (VAS) at Day 57 assuming a true difference (NOV03 minus saline) of -10, a common standard deviation of 28, and a two-sided alpha = 0.05. Accounting for an assumed 10% subject discontinuation rate, approximately 560 subjects (280 subject each arm) will be randomly assigned to trial treatment such that approximately 250 evaluable participants per arm complete the trial.

Therefore, assuming independence between tCFS score and Dryness Score (VAS), 250 FAS subjects per treatment group at Day 57 yields $97.9\% * 97.9\% = 95.8\%$ power to reject both H_{01} and H_{02} .

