8.4 Examination Procedures

8.4.1 Procedures to be performed at each trial visit with regard to trial objective(s)

See [Appendix 1](#) for a schedule of visits and measurements in recommended order. [Appendix 3](#) describes the eye examinations. These should not be done earlier than 2 hours after IMP instillation. If possible the same investigator/coordinator should perform the assessments for an individual subject. Primary endpoint assessments at Baseline Visit 1 (Day 1) and Visit 4 (Day 57) should be done preferably on the same time of the day.

The dedicated dosing coordinator will perform tasks as described in IMP Masking7.4.

Visit 0 (Up to 14 days before Visit 1): Screening

- Informed consent / HIPAA;
- Demographic data and medical / medication history;
- Review of inclusion / exclusion criteria;
- Urine pregnancy test;
- Ocular Surface Disease Index (OSDI[©]) questionnaire;
- Visual acuity (ETDRS);
- Slit-Lamp biomicroscopy;
- Tear Film Break-up Time (TFBUT);
- Fluorescein staining (NEI scale);
- Meibomian gland assessment (MGD score) (wait 5 min prior start of Schirmer's test);
- Schirmer's test I (without anesthesia);
- Intraocular pressure;
- Dilated fundoscopy;
- Non-leading AE questioning (Adverse event query);
- Qualified subjects will be scheduled for Visit 1.

Visit 1 (Day 1): Baseline/Randomization

- Previous/Concomitant Medication;
- Review of inclusion / exclusion criteria;
- Urine pregnancy test;
- Dryness Score (VAS Severity of Dryness);
- VAS for burning/stinging, sticky feeling, foreign body sensation, itching, blurred vision, sensitivity to light, pain, frequency of dryness, and awareness of dry eye symptoms;
- Ocular Surface Disease Index (OSDI[©]) questionnaire;
- Visual acuity (ETDRS);
- Slit-Lamp biomicroscopy;
- Tear Film Break-up Time (TFBUT);
- Fluorescein staining (NEI scale);
- Meibomian gland assessment (MGD score) (wait 5 min before start of Schirmer's test);
- Schirmer's test I (without anesthesia);
- Randomization;
- In-office dose of IMP;
- Instillation comfort questionnaire;
- Non-leading AE questioning (Adverse event query);
- Dispensation of dosing diary
- Drug dispensation of one kit for self-administered dosing until Visit 2;
 - Subjects will be instructed on how to administer IMP;
 - Subjects will be instructed to dose with IMP on the day of their next visit at least 2 hours before the start of their visit (Visit 2);
 - Subjects will be instructed on how to complete the dosing diary.

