- **Treatment assignment method** - Subjects who meet all inclusion and exclusion criteria at Visits 0 and 1 will be randomized to a treatment group NOV03 (100% perfluorohexyloctane) or saline (0.6% sodium chloride solution) in a 1:1 ratio stratified by clinical site and dryness score <70 vs ≥ 70 (VAS) at baseline (Visit 1). Subjects who fail to qualify for the trial at screening may be rescreened (see Section 6.2).

An Interactive Response System (IRS) will be used to account for the stratification factors while assigning the drug kit numbers at Visits 1, 2 and 3. Each treatment group of this trial will consist of approximately 280 subjects, such that approximately 250 evaluable subjects per arm complete the trial, for an estimated total of 560 randomized subjects. Specifically, the treatments are defined as follows:

- Treatment 1: NOV03 (100% perfluorohexyloctane), 4 times daily (QID)
- Treatment 2: Saline (0.6% sodium chloride solution), QID
- **Packaging and labeling** - The IMP will be labelled according to the legal requirements and packaged into individual subject kits, each containing 2 bottles of NOV03 or saline solution. In compliance with the Code of Federal Regulations 21 part 312, section 312.6, the labels for the IMP shall be comprised of:
 - Protocol number
 - Kit number
 - Investigational new drug statement
 - Storage conditions
 - Name and address of the sponsor
- **Trial configuration** - This is a parallel trial design (NCI Preferred Term ‘Parallel Study’). Subjects will be randomized to either NOV03 QID or saline QID in a 1:1 ratio. Subjects will self-administer one drop of masked investigation product in the lower cul-de-sac of each eye QID at approximately the same time e.g., morning, lunch time/midday, afternoon/early evening, and at bedtime. *Note:* if a dose is missed, the next dose should be administered on time.
- **Type of control used** - This is a saline-controlled (NCI Preferred Term ‘Placebo Control’), superiority trial.
- **Duration of the trial** - The estimated trial duration is approximately 8 months, from first subject first visit to last subject last visit. An individual subject’s participation will involve 5 visits over approximately a 10-week period, including screening. After the trial, subjects will be treated according to standard of care, at the discretion of the treating physician.

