Least squares mean for each treatment group and for the difference between treatment groups will be presented from each model together with two-sided p-values (used for primary inference) and 95% confidence intervals.

Sample SAS ANCOVA code:

```
PROC GLM DATA=INDATA;
  CLASS <TREATMENT>;
  MODEL <ENDPOINT>=<TREATMENT> <BASELINE>;
  LSMEANS <TREATMENT> / CL ALPHA=0.05;
  LSMEANS <TREATMENT> / PDIFF CL ALPHA=0.05;
RUN;
```

Additional robustness analyses will include repeating the primary analysis on the PPS; the FAS imputing missing data using last observation carried forward (LOCF); the FAS imputing missing data using MCMC multiple imputation methodology under different assumptions of missingness (at random and not at random) each using 30 imputed values.

Sample SAS MCMC MI (missing at random):

```
PROC MI DATA=INDATA SEED=97656 OUT=OUTDATA MINIMUM=0 MAXIMUM=3 ROUND=1
NIMPUTE=30;
  MCMC INITIAL=EM;
  BY <TREATMENT>;
  VAR <BASELINE> <PARAMETER>;
RUN;
```

Where <PARAMETER> has 5 levels and refers to the CFS for each region (inferior, superior, central, temporal, and nasal).

Sample SAS MCMC MI (not missing at random):

```
PROC MI DATA=INDATA SEED=36797 OUT=MDATA MINIMUM=0 MAXIMUM=3 ROUND=1
NIMPUTE=30;
```

```
  MCMC IMPUTE=MONOTONE;
  VAR <BASELINE> <PARAMETER>;
RUN;
```

```
PROC MI DATA=MDATA SEED=38549 OUT=OUTDATA2 MINIMUM=. 0 0 MAXIMUM=. 3 3
ROUND=. 1 1;
  CLASS <TREATMENT>;
  MONOTONE REG(<PARAMETER>=<BASELINE> / DETAILS);
  MNAR MODEL(<PARAMETER> / MODELOBs=(<TREATMENT>='Saline'));
  VAR <TREATMENT> <BASELINE> <PARAMETER>;
RUN;
```

Where <PARAMETER> has 5 levels and refers to the CFS for each region (inferior, superior, central, temporal, and nasal).

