6.5.8.8 Multicenter Studies

No formal by site analyses will be conducted. Analyses by sites for sites with a sufficient number of subjects can be conducted in an adhoc manner to confirm the uniformity of the overall results.

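### Randomisation is stratified by site and baseline dryness, but the models leave out site throughout and dryness almost everywhere, so intervals are too wide if these factors predict outcome

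*SAP*

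**What the plan says.** SAP section 4 allocates subjects in a "1:1 ratio stratified by clinical site and dryness score" (below 70 versus 70 or more at Visit 1). Protocol 4.1 and 4.4 agree. The SAP expects about 26 sites and the protocol about 29, so there are 52 to 58 site-by-dryness cells.

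SAP 6.5.8.5 then says: "The analyses will not be adjusted for the stratification factors". The model specifications follow this:

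- **Primary ANCOVA.** Protocol 10.4.5 analyses each primary endpoint "using an ANCOVA model with terms for baseline value, and treatment". The SAP 6.5.7.3 code is "MODEL <ENDPOINT>=<TREATMENT> <BASELINE>".
- **Repeated-measures sensitivity model.** The SAP 6.5.7.6.1 code is "MODEL <ENDPOINT>=<TREATMENT> <VISIT> <TREATMENT>*<VISIT> <BASELINE>", with subject as the random effect.
- **Responder analyses.** The logistic models are described as adjusting for baseline tCFS only (SAP 6.5.7.4.2).
- **t-test, Wilcoxon and chi-squared analyses.** These carry no covariates.
- **Sites.** SAP 6.5.8.8: "No formal by site analyses will be conducted". By-site work is left to ad hoc analysis.

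Site is therefore in none of these analyses. Baseline Dryness Score enters only as the continuous baseline of the Dryness Score ANCOVA and repeated-measures models. The visible text gives no reason for the omission. Some exploratory text is redacted, but the sentence in 6.5.8.5 is general.

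**The concern.** Stratified allocation balances the arms within each site and dryness level, which takes between-stratum variation out of the treatment difference. A model without the strata leaves that variation in its residual error, so it reports a standard error larger than the true one.

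What is lost differs by endpoint. The Dryness Score ANCOVA already has continuous baseline dryness, which largely covers the two-level stratum, so mainly site is missing. The models for tCFS, central CFS and burning/stinging have neither factor.

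For tCFS, part of a site effect is already handled. If a site's graders score consistently high or low, change from baseline with a baseline covariate absorbs some of that shift, and Protocol 8.4.1 helps: "If possible the same investigator/coordinator should perform the assessments for an individual subject". What remains is the unabsorbed part of the shift plus any between-site difference in change.

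At stake are correctly sized confidence intervals and some power, chiefly for the four secondary endpoints. These are tested in fixed sequence, so one miss ends the testing of everything below it.

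**Working it through.** **Plan's own figures (Protocol 10.3).** Inputs: 250 per arm, two-sided alpha 0.05, difference 1.0 with SD 2.8 (tCFS), difference 10 with SD 28 (Dryness Score). Both standardised effects are 1/2.8 = 10/28 = 0.357.

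- SE for tCFS = 2.8 × √(2/250) = 0.2504, and 1.0/0.2504 = 3.993.
- Power = Φ(3.993 − 1.960) = 97.9% for each endpoint. The noncentral t gives 97.86%.
- Joint power under independence = 0.979² = 95.8%.

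The stated power reproduces. The planning SDs rest on NVU-002 estimates from an ANCOVA with "baseline as a covariate and treatment as the fixed effect from NVU-002" (Protocol synopsis). They contain no site or stratum adjustment, so the stated power is not overstated.

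**Effect of leaving the factors out.** Let R be the share of the model's residual variance explained by site and dryness stratum. The documents do not give R, so a range is assumed. With allocation balanced within strata:

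- true variance of the difference = (1 − R) × 2SD²/n, against a reported 2SD²/n
- reported SE / true SE = 1/√(1 − R)
- actual alpha = 2 × [1 − Φ(1.960/√(1 − R))]
- power as planned = Φ[(m − 1.960)/√(1 − R)]; power adjusted = Φ[m/√(1 − R) − 1.960], where m = standardised effect × √(250/2)

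For tCFS, m = 3.993. No effect size is stated for the secondaries, so 0.25 is assumed, giving m = 2.795.

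| R | SE too large by | Actual alpha | tCFS power, planned → adjusted | Power at effect 0.25, planned → adjusted |
|---|---|---|---|---|
| 1% | 0.5% | 4.9% | 97.95 → 98.00% | 79.9 → 80.2% |
| 2% | 1.0% | 4.8% | 98.0 → 98.1% | 80.1 → 80.6% |
| 5% | 2.6% | 4.4% | 98.2 → 98.4% | 80.4 → 81.8% |
| 10% | 5.4% | 3.9% | 98.4 → 98.8% | 81.1 → 83.8% |
| 20% | 11.8% | 2.8% | 98.9 → 99.4% | 82.5 → 87.8% |

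For tCFS, the power forgone equals that of 0.5, 1.0, 2.5, 5.0 and 10.1% of the sample, in row order.

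As an illustration of the fixed sequence, take four independent tests at the assumed effect of 0.25. The chance of passing all four rises from 0.804⁴ = 42% to 0.818⁴ = 45% at R = 5%, and from 0.811⁴ = 43% to 0.838⁴ = 49% at R = 10%.

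**How large R could be from a constant site grading shift.** Assume the shift holds a share g of baseline variance, with a within-site baseline to Day 57 correlation of 0.5 and equal variances. The fitted slope is b = 0.5 + 0.5g, so R = 1 − (1 − g)(1 − 0.5²)/(1 − b²).

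- g = 10%: b = 0.55, R = 1 − 0.675/0.6975 = 3.2%.
- g = 20%: b = 0.60, R = 1 − 0.600/0.640 = 6.3%.

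Reaching R of 10 to 20% needs real between-site differences in change, or a dryness stratum that predicts the non-dryness endpoints.

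**Simulation checks** (permuted blocks of 4 within cells; the block size is assumed).

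- *560 subjects, 26 or 29 sites, 4,800 trials per setting, Monte Carlo error about 0.003.* At R about 9.5%, alpha was 0.037 unadjusted and 0.048 with fixed or random site. At R about 19%, it was 0.026 unadjusted, 0.045 with fixed site and 0.046 with random site; the mean SE was 0.0815 unadjusted against 0.0734 adjusted (ratio 1.11). At R about 3% and 6%, unadjusted alpha was 0.051 and 0.047, not distinguishable from 5%.
- *500 subjects, 29 sites, R split equally between site and stratum, 6,000 null trials per setting.* Alpha unadjusted versus adjusted was 0.051 vs 0.050 at R = 0, 0.042 vs 0.055 at 10% and 0.031 vs 0.052 at 20%. Mean interval widths were 0.985 vs 0.989, 0.984 vs 0.937 and 0.984 vs 0.884. Adjustment costs almost nothing when the factors do not matter.

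**The case against.** The strongest reply is that this is an explicit, consistent and valid choice. Protocol and SAP agree, the planning SDs come from the same model, any error runs against the sponsor, and the primary endpoints gain at most about half a point of power. The only mechanism worked through, a constant grading shift, leaves R near 3 to 6%, where simulated alpha cannot be told from 5%. The larger figures rest on an R, and the secondary power on an effect size, that no document supplies. All of this stands. It makes the point one of efficiency and interval calibration, not validity.

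A second reply is that the protocol plans for 10% discontinuation, and at 5% or more the primary analysis moves to imputation by treatment arm without site. Adjusting the analysis model alone might then gain little or cause trouble. This was tested by simulating 10% missing data with that imputation. At R = 10% and 20%, the site-adjusted analysis held alpha at 0.050 and 0.048, against 0.044 and 0.033 unadjusted, and its SE was still about 3.6% and 7.2% smaller. The gain is diluted but not lost.

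Third, a random site term brings its own details, such as convergence and zero site variance, and the responder models would remain unadjusted. Both are fair but minor, and neither makes the change unsound.

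**Conclusion.** The concern holds. The plan stratifies on two factors, then omits site from every visible analysis and dryness from all but the Dryness Score's own ANCOVA and repeated-measures models, with no stratum-adjusted sensitivity analysis.

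If the factors predict outcome, intervals are too wide: by 1.0% at R = 2%, 5.4% at 10% and 11.8% at 20%. Tests are correspondingly conservative. False positives are not inflated and the stated power stands. The practical loss falls on the gated secondaries: 1.4 points of power at R = 5% and 2.7 at R = 10%, if their standardised effect is 0.25.

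This rests on the assumed R and on near-balance within cells. With only about 10 subjects per cell, balance is imperfect and the real conservatism may be slightly less than the formula gives. The change is worth making because it is cheap and costs almost nothing if R is zero.

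**What to change.** Before unmasking, replace the no-adjustment sentence in SAP 6.5.8.5 with wording such as:

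> The ANCOVA for the primary, secondary and other quantitative endpoints will include baseline value, treatment, the randomisation stratum Dryness Score <70 vs ≥70 (omitted in the Dryness Score models, which carry continuous baseline dryness) and clinical site as a random intercept. The ANCOVA with baseline and treatment only will be reported as a sensitivity analysis.

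Add the same terms to the repeated-measures model, and align Protocol 10.4.5. Leave the by-treatment imputation models unchanged, because each arm has only about 10 subjects per site (280/29 = 9.7 to 280/26 = 10.8). State what is done if the site variance is estimated as zero or the model does not converge, and say whether the responder models stay as they are.

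The cost is wording in both documents and a move of the ANCOVA code from PROC GLM to PROC MIXED. A random intercept needs no site-pooling rule. Fixed site effects would use about 26 to 29 of roughly 500 degrees of freedom and need a pooling rule set before unmasking. If the sponsor prefers to keep the present primary model, a pre-specified sensitivity analysis with both factors is the minimum.
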